**Table 1: Skin Phototoxicity Grading**

Toxicity Grade: Erythema and/or edema	Severity
Grade 0	No apparent reaction
Grade I	Mild
Grade II	Moderate
Grade III	Severe with edema
Grade IV	Life-threatening with vesication

## 4. STUDY ENDPOINTS AND DEFINITION

This is an exploratory study to confirm the low-level systemic exposure to hypericin and the associated potential for any ECG changes as well as obtaining additional information on patient benefit including, but not limited to, lesion response to HyBryte photodynamic therapy utilizing the Daavlin 7 Series phototherapy device.

### 4.1. Primary Endpoints

Serial assessments of ECG (including QT interval and QT interval corrected for heart rate using both the Bazett's and Fridericia's formulas) will be obtained at the same timepoints as serum hypericin samples as follows:

- Baseline prior to drug application
- Week 4, Session 2 obtained immediately before and 2 hours after the light session
- Week 6, Session 2 obtained immediately before the light session
- Week 8, Session 2 Light Session visit obtained immediately before and 2 hours after the light session
- End of Study during the follow-up visit

Serial measurements of serum hypericin levels obtained at the following timepoints will be correlated with the cumulative amount of drug applied by the patient estimated by weighing the drug jars at each light session:

- Baseline prior to drug application
- Week 4, Session 2 obtained immediately before and 2 hours after the light session
- Week 6, Session 2 obtained immediately before the light session
- Week 8, Session 2 Drug Application visit immediately prior to the drug application
- Week 8, Session 2 Light Session visit obtained immediately before and 2 hours after the light session
- End of Study during the follow-up visit

### 4.2. Secondary Endpoints

Routine safety laboratory investigations and vitals will be obtained at Baseline prior to drug application, at Week 8, Session 2 Light Session visit prior to light therapy and 2 weeks after the completion of therapy (End of Study visit).

### 4.3. Patient Treatment Response Parameters

Given the small sample size in this open-label study, patient treatment response will be summarized as changes in disease status from Baseline to the end of treatment:

- Skindex-29 quality of life questionnaire
- Visual Assessment Scale of itch (VASitch)
- CAILS score of the 3 prospectively chosen index lesions
- Physician Global Assessment (PGA)
- modified Severity Weighted Assessment Tool (mSWAT)

In addition, the light dose schedules optimized for each patient will be characterized.

### 4.4. Study Endpoint Definition

#### 4.4.1 Electrocardiograms (ECGs)

12-lead ECGs, including QT interval measurement, will be done at Baseline (prior to drug application), Week 4, Session 2 (immediately prior to and 2 hours after the light session), Week 6, Session 2 (immediately prior to the light session), Week 8, Session 2 Light Session Visit (immediately prior to and 2 hours after the light session), and at the End of Study visit. ECGs will be interpreted by site personnel trained in the evaluation of ECGs for any interval changes.

QT intervals will be measured on each ECG. Heart rate corrected QT intervals will be calculated using the following 2 standard correction equations:

*Bazett's Formula:*

$$QT_{cB} = QT_m / \text{square root of RR}$$

Where  $QT_{cB}$  represents the Bazett's corrected QT interval,  $QT_m$  is the measured QT interval, and RR is the time interval between 2 consecutive QRS complexes in seconds.

*Fridericia's Formula:*

$$QT_{cFri} = QT_m / \text{cube root of RR}$$

Where  $QT_{cFri}$  represents the Fridericia's corrected QT interval,  $QT_m$  is the measured QT interval, and RR is the time interval between 2 consecutive QRS complexes in seconds.

#### 4.4.2 Hypericin blood levels

Blood samples for pharmacokinetic analysis will be collected at the following timepoints:

- Baseline, prior to drug application

- Week 4 Session 2, prior to light session
- Week 4 Session 2, 2 hours after completion of the light session
- Week 6 Session 2, prior to the light session
- Week 8 Session 2 Drug Application visit, prior to drug application
- Week 8 Session 2 Light Session visit, prior to light session
- Week 8 Session 2 Light Session visit, 2 hours after completion of the light session
- End of Study follow-up visit

Blood samples will be collected with K2EDTA tubes and mixed (inverting top to bottom) at least 5 times after collection. Tubes will be placed on wet ice pending transfer to labeled 2 mL amber vials or tubes and then frozen (temperature  $\leq -60^{\circ}\text{C}$ ). The times that samples are collected and frozen must be noted. Blood will be processed and shipped to the central laboratory, Syneos Health.

#### **4.4.3 Clinical Laboratory Tests**

##### **4.4.3.1. Hematology Tests**

The hematology panel will be performed on blood obtained at Baseline, Week 8 Session 2 Light Session visit prior to the light session, and End of Study. The panel will consist of the following tests:

- Red blood cell count (RBC)
- Hematocrit
- Hemoglobin
- Mean corpuscular volume (MCV)
- Mean corpuscular hemoglobin (MCH)
- Mean corpuscular hemoglobin concentration (MCHC)
- Platelet count
- White blood cell count (WBC)
- Percent and absolute neutrophil count
- Percent and absolute lymphocyte count
- Percent and absolute monocyte count
- Percent and absolute eosinophil count
- Percent and absolute basophil count

#### 4.4.3.2. Clinical Chemistry Tests

The clinical chemistry panel will be performed on blood obtained at Baseline, Week 8 Session 2 Light Session visit prior to the light session and during the End of Study follow-up visit. The panel will consist of the following tests:

- Serum sodium
- Serum potassium
- Serum chloride
- Serum bicarbonate (CO2)
- Alanine aminotransferase (ALT)
- Aspartate aminotransferase (AST)
- Total bilirubin
- Total protein
- Serum creatinine
- Blood urea nitrogen (BUN)
- Alkaline phosphatase

#### 4.4.4 Vital Signs

Vital signs will be obtained by site personnel at Baseline, Week 8 Session 2 Light Session visit prior to the light session and during the End of Study follow-up visit. Vital signs obtained will consist of:

- Resting Blood Pressure
- Heart Rate
- Respiratory Rate

#### 4.4.5 Quality of Life Questionnaire

The Skindex-29, a self-administered survey instrument to measure the effects of skin disease on patients' quality of life will be administered at Baseline and at Week 8 Session 2 Light Session visit. Patients will complete the form on their own and site personnel will review and assure that the form is complete.

Each questionnaire item is answered in a 5-point Likert-type scale and these answers will be transformed into a linear scale of 100 (0 = no effect; 100 = effect experienced all the time) using the following item scores:

Never = 0

Rarely = 25

Sometimes = 50

Often = 75

All the time = 100

The following criteria will be used for interpretation:

- If responses to more than 25% of items are missing overall, the questionnaire will be considered “missing”.
- If any domain scale has more than 25% of the responses missing, the score for that domain will be considered “missing”.
- Domain scale scores are the average of non-missing items in a given domain scale.
- An item with multiple answers is considered “missing”.

Individual questions will be grouped into 3 domains as follows:

Domain	Number of Items	Cluster Items
Emotions	10	3, 6, 9, 12, 13; 15; 21, 23, 26, 28
Symptoms	7	1, 7, 10, 16, 19, 24, 27
Functioning	12	2, 4, 5, 8, 11, 14, 17, 20, 22, 25, 29, 30

For all domains, a higher score is associated with higher impact of disease.

#### 4.4.6 VASitch

The Visual Analog Score for Itch (VASitch) is a patient reported outcome measurement of the degree of itchiness that the patient experienced over the preceding 24 hours and is administered at Baseline, each light treatment and the End of Study visit. Patients will be instructed to place a vertical mark on a 10 cm line with a 0 (none) at the right side and a 10 (the worst itch you can imagine) at the left indicating the amount of itch that they have experienced over the preceding day. The score is recorded as the distance in centimeters (to 1 decimal place) between the 0 mark and the vertical line the patient drew.

Patient responses will be categorized as shown in [Table 2](#), with scores rounded to the nearest whole number.

**Table 2: VASitch Grading**

VAS itch Score	Category of Itch
0	no pruritus
<3	mild pruritus
3 to <7	moderate pruritus
≥7 to <9	severe pruritus
≥9	very severe pruritus

**4.4.7 Composite Assessment of Lesions Severity (CAILS) Score**

The CAILS score will be assessed for the 3 prospectively identified representative lesions at Baseline and at the End of Study visit. CAILS score will be calculated by assessing the index lesions for erythema, scaling, plaque elevation and involved surface area using the grading scale shown in [Table 3](#) for each of the index lesions. Each of the assessments and the total score for each evaluated lesion will be recorded in the eCRF. The total CAILS score will be calculated by adding the scores of all evaluated lesions together.

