### **5.3.10 Week 10, Follow-up visit/End of Study**

During the last visit of the study, expected to occur 2 weeks following the final light treatment, the following assessments will be performed:

The patient will complete the VASitch form and the data transcribed into the eCRF.

Vitals taken (heart rate, respiratory rate, and sitting blood pressure).

Hematology panel drawn.

Clinical chemistry panel drawn.

5 mL of blood obtained and processed for serum hypericin levels.

CAILS scores for the 3 index lesions will be measured and recorded.

The mSWAT and PGA scores will be assessed and recorded.

A 12-lead ECG obtained including QT interval measurements.

Patients will be asked about any AEs experienced since the last light session and these will be recorded in the eCRF. Information on all unresolved, previously reported AEs will be obtained.

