#### **5.4 Premature Discontinuation**

Patients have the right to withdraw from this trial at any time (as described in the informed consent document) without prejudice to further care. An investigator may withdraw a patient from the study at any time for any of the following reasons:

- The patient withdraws his/her consent or refuses follow-up evaluations.
- The patient is lost to follow-up and will not attend further study visits.
- The investigator determines that further participation would be detrimental to the patient's health or well-being.
- The patient fails to comply with the study requirements so as to cause harm to self or seriously interfere with the validity of the study results.
- The female patient becomes pregnant during the treatment period. In this case, treatment should be halted and the patient followed until the end of the pregnancy. If a child is born, the infant should be followed through at least 6 months of age.
  - At the discretion of the site investigator if he/she feels that it is in the best medical interest of the patient.

Patients withdrawn from the study will have as many of the trial assessments completed as the patient permits including blood tests and lesion evaluations.

Patients withdrawn from the study may be replaced up to a total of 8 subjects provided that both the PI and the Soligenix Medical Monitor agree that the reasons for withdrawal do not suggest a change in the risk assessment of the HyBryte therapy.

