## 5.5. Demographics and Other Baseline Characteristics

Demographic data will be summarized descriptively and include:

- Age
- Sex
- Race
- Ethnic group

Listings of demographic data characteristics will be provided for each patient and summarized across the study population.

Baseline disease characteristics will be summarized descriptively and will include:

- CTCL Stage (IB, IIA)
- Number of previous CTCL treatments
- Time since original diagnosis to randomization
- Extent of disease (percent body area with lesions)
- Cumulative CAILS score for the 3 index lesions at Baseline
- Baseline VASitch score
- Baseline mSWAT
- Baseline Skindex-29 QoL score

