### 6.3. Effectiveness Outcomes

Descriptive analyses will include:

- Percent of cumulative CAILS score for index lesion as a proportion of the baseline CAILS score ([cumulative score at End of Study] / [cumulative score at Baseline] \* 100). The average, standard deviation and range of the %response at Week 10 will be summarized.
- Mean, standard deviation and range of the PGA score at End of Study.

- Mean, standard deviation and range of the mSWAT score at Baseline and End of Study.
- Mean, standard deviation and range of the change in the mSWAT score (calculated as the mSWAT score at End of Study – mSWAT score at Baseline).
- Mean, standard deviation and range of the Skindex 29 score and its 3 domains (emotions, symptoms, functioning) at Baseline and Week 8.
- Mean, standard deviation and range of the change in Skindex 29 score and its 3 domains.
- Mean, standard deviation and range of the VASitch score at baseline, each light treatment and the end of study visit.
- Shift analysis of VASitch categories (none/mild/moderate/severe) over all study timepoints.
- Mean, standard deviation and range for the treatment visit at which the maximum light dose was obtained.
- Mean, standard deviation and range for the maximum light dose that was used.
- Listing of changes of drug used (change in drug jar weight)

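### The CAILS percentage of baseline does not require the same index lesions in both totals, so an uncleared lesion left unscored at End of Study makes the result look better

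*SAP*

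**What the plan says.** - **The total.** SAP 4.4.7 says: "The total CAILS score will be calculated by adding the scores of all evaluated lesions together". Protocol 6.8 has the same rule, so the protocol does not change it.
- **Lesions and visits.** SAP 4.4.7: "The CAILS score will be assessed for the 3 prospectively identified representative lesions at Baseline and at the End of Study visit". Protocol 5.3.10 confirms for the last visit: "CAILS scores for the 3 index lesions will be measured and recorded".
- **The outcome.** SAP 6.3 takes the ratio "cumulative score at End of Study] / [cumulative score at Baseline", multiplied by 100, and adds: "The average, standard deviation and range of the %response at Week 10 will be summarized".
- **The Baseline total.** SAP 5.5 lists "Cumulative CAILS score for the 3 index lesions at Baseline", so the denominator is meant to cover three lesions.
- **Partial data.** Protocol 5.4: "Patients withdrawn from the study will have as many of the trial assessments completed as the patient permits including blood tests and lesion evaluations". SAP 5.2 reports every enrolled patient for whatever periods have data.
- **Missing-data rules.** SAP Appendix 1 deals with adverse event severity, causality and dates, medication dates, and laboratory values. SAP 4.4.5 gives Skindex-29 its own rule for missing items. Neither document has such a rule for CAILS.

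**The concern.** A sum over whichever lesions were evaluated depends on how many were evaluated. A ratio of two such sums is interpretable only if both cover the same lesions, and the SAP does not make that a condition. It also does not rescale for the number of lesions scored, or set the ratio to missing when a lesion is absent.

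If one lesion is unscored at End of Study, the numerator covers two lesions and the denominator three. A cleared lesion properly contributes 0, so the total alone cannot separate an unscored lesion from a cleared one.

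What is at stake is the descriptive account of lesion response. With about six patients and no control arm, one affected patient visibly moves the mean, and there is no comparison group to offset it. If the rule is settled only once it is known which lesions are missing, the choice becomes data-driven.

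**Working it through.** **Inputs from the documents.** Three index lesions (SAP 4.4.7); the sum rule (SAP 4.4.7, Protocol 6.8); the ratio (SAP 6.3); approximately 6 subjects (Protocol 5.1), up to 8 with replacement (Protocol 5.4). The maximum score per lesion is 8 + 8 + 3 + 18 = 37 (SAP Table 3). The documents give no figure of their own on this point, so there is nothing to reproduce.

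**Assumptions.** The documents give no lesion scores and no rate of unscored lesions. All lesion scores below are assumed, and the results are conditional on one lesion being unscored.

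**Formula.** Let b1, b2, b3 be the Baseline scores with sum B, and e1, e2, e3 the true End of Study scores. The intended ratio is 100 × (e1 + e2 + e3)/B. If lesion k is unscored at End of Study, the sum as worded gives a ratio lower by 100 × e_k/B. The error is therefore zero if lesion k has truly cleared (e_k = 0), and otherwise always lowers the ratio, toward improvement.

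**One unchanged patient, one lesion unscored at End of Study (correct ratio 100%):**

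| Assumed scores | Ratio as worded | Apparent improvement |
|---|---|---|
| 12, 12, 12 | 24/36 = 66.7% | 33.3% |
| 10, 12, 14 | 26/36 = 72.2% to 22/36 = 61.1% | 27.8% to 38.9% |
| 8, 12, 20 | 32/40 = 80.0% to 20/40 = 50.0% | 20.0% to 50.0% |

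- For any scores within two-fold of each other, the apparent improvement lies between 1/(1+2+2) = 20% and 2/(2+1+1) = 50%.
- If each lesion is equally likely to be the one missed, the average is (b1 + b2 + b3)/(3B) = 33.3%, whatever the scores.
- At the extremes of the scale, with at least 1 point per lesion, the range is 1/75 = 1.3% to 37/39 = 94.9%.

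**Group mean, all patients unchanged, one affected (equal scores):**

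- n = 6: (5 × 100 + 66.7)/6 = 94.4%, a shift of 5.6 points. The SD becomes 13.6, where it should be 0.
- n = 8: (7 × 100 + 66.7)/8 = 95.8%, a shift of 4.2 points.
- n = 6 with scores within two-fold: 20/6 = 3.3 to 50/6 = 8.3 points. At the extremes of the scale: 1.3/6 = 0.2 to 94.9/6 = 15.8 points.

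**Omission at Baseline instead.** Equal unchanged scores with one lesion missed at Baseline give 36/24 = 150%, an apparent worsening.

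**After the fix.** Using only lesions scored at both visits, the unchanged patient with one lesion unscored at End of Study has 24/24 = 100%.

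**The case against.** The best reply is that the rule, read in context, already means the three index lesions. The sum follows directly on a sentence naming them, SAP 5.5 ties the Baseline total to all three, and Protocol 5.3.10 requires all three to be scored at the last visit. On that reading the ratio simply cannot be computed when one is absent. The trigger is also unlikely: three charted, numbered lesions are scored at a single visit, and a patient who withdraws is more likely to lose the whole assessment than one lesion of three. Finally, each lesion's score goes into the eCRF and Protocol 10.2 plans listings per patient, so a gap would be easy to see among about six patients.

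Much of this stands. The plan is for complete scoring, and the documents give no reason to expect many gaps. But the reading that makes the ratio non-computable is not written anywhere. The wording sums what was evaluated, Protocol 5.4 contemplates incomplete lesion evaluations, and SAP 5.2 favours reporting what is available. A programmer following the text would produce the two-over-three ratio. Seeing the gap in a listing does not correct the summary.

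Two stronger readings are tempting and not supported. A reader might infer that the SAP imputes zero for an unscored lesion. It does not; zero is only what the sum amounts to when a term is left out. A reader might also infer that any unscored lesion favours the treatment. It does not: one that had truly cleared causes no error, and one missed at Baseline pushes the ratio upward.

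**Conclusion.** The point holds as a minor gap in the definition. As worded, the CAILS ratio can compare two lesions with three, and no other section prevents it. The bias is toward improvement when an uncleared lesion is unscored at End of Study.

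The headline size, 66.7% instead of 100% and a shift of about 5.6 points in a mean of six, rests on assumed equal and unchanged lesion scores and on exactly one affected patient. A reader might take one-third as the size for every such patient. It is exact for equal scores and an average over which lesion is missed, but individual patients can fall well to either side. How often it would happen cannot be estimated from the documents. When every index lesion is scored at both visits, there is no error.

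The consequence is confined to one descriptive outcome, listed under the secondary objectives in SAP 2.2, with no test or decision rule attached. Protocol 10.1 rules out efficacy analyses. The primary ECG and hypericin endpoints are unaffected.

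**What to change.** Add one sentence to SAP 4.4.7 and refer to it in SAP 6.3: the End of Study and Baseline totals used in the ratio include only index lesions scored at both visits. List the number of lesions contributing for each patient beside the result.

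The scale already has a 0 level for every component, so a cleared lesion should be entered as 0 and not left blank. This matters because the matched-lesion ratio would otherwise drop a cleared lesion and understate response.

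Setting the ratio to missing when any index lesion is unscored would also remove the artefact, but loses the patient from a very small summary.

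The cost is the sentence itself. Lesion-level scores are already recorded in the eCRF, no new data are needed, and nothing changes when all three lesions are scored.

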**Table 3: Composite Assessment of Index Lesion Severity**

ERYTHEMA	
Score	Description
0	No evidence of erythema, possible brown hyperpigmentation
1	*
2	Mild: Light red lesion
3	*
4	Moderate: Red lesion
5	*
6	Severe: Very red lesion
7	*
8	Very severe: Extremely red lesion

  

SCALING	
Score	Description
0	No evidence of scaling on lesion
1	*
2	Mild: Mainly fine scales: lesion partially covered
3	*
4	Moderate: Somewhat coarser scales: lesion partially covered
5	*
6	Severe: Coarse, thick scales; virtually all of the lesion covered; rough surface
7	*
8	Very severe: Coarse, very thick scales; all of the lesion covered very rough surface

  

PLAQUE ELEVATION	
SOLIGENIX	Confidential and Proprietary

**Table 3: Composite Assessment of Index Lesion Severity**

Score	Description
0	0 mm: No evidence of plaque above normal skin level
1	Mild elevation
2	Moderate elevation
3	Marked elevation
SURFACE AREA	Longest diameter and the longest diameter perpendicular to this diameter of each index lesion will be measured to the nearest millimeter. The lesion area will be the product of these two diameters.
Score	Area
0	0 cm 
1	>0 and ≤4 cm 
2	>4 and ≤10 cm 
3	>10 and ≤16 cm 
4	>16 and ≤25 cm 
5	>25 and ≤35 cm 
6	>35 and ≤45 cm 
7	>45 and ≤55 cm 
8	>55 and ≤70 cm 
9	>70 and ≤90 cm 
10	>90 and ≤110 cm 
11	>110 and ≤130 cm 
12	>130 and ≤155 cm 
13	>155 and ≤180 cm 
14	>180 and ≤210 cm 
15	>210 and ≤240 cm 
16	>240 and ≤270 cm 
17	>270 and ≤300 cm 
18	>300 cm 

#### 4.4.8 The Physician Global Assessment (PGA)

The PGA represents the investigator's assessment of the overall extent of improvement or worsening of the patient's cutaneous disease compared with baseline as shown in [Table 4](#). This assessment is designed to consider all cutaneous lesions, including both index and non-index lesions. PGA score will be assessed at End of Study.

**Table 4: Physician Global Assessment**

Grade	Description
0 completely clear	No evidence of disease; 100% improvement
1 almost clear	Very obvious improvement (≥90% to <100%); only traces of disease remain

Grade	Description
2 marked improvement	Significant improvement ( $\geq 50$ to $<90\%$ clear); some evidence of disease remains
3 moderate improvement	Intermediate between marked and mild ( $\geq 25\%$ to $<50\%$ )
4 slight improvement	$\geq 10\%$ to $<25\%$ ; significant evidence of disease remains
5 no change	Disease has not changed significantly from baseline (10 to -25%)
6 condition worse	Disease is worse than baseline by $\geq 25\%$

